## 10.2 Statistical Analysis Plan

### *Primary analysis of Subaim 1A*

We will compare pre-transplant insulin secretion (first- and second-phase GSIS) among patients who do or do not go on to develop PTDM. Wilcoxon rank sum test will be applied to compare the population mean difference between these two groups.

Multivariable logistic regression will evaluate whether GSIS is an independent predictor of PTDM after adjusting for the following covariates: gender, conditioning (ablative vs. reduced intensity), or acute GVHD requiring steroids. The estimated OR and 95% CI of the OR will be provided to measure the effect of the association. We will take a similar approach for the primary analysis of Aims 1B and 2 which will compare post-transplant total glucagon secretion during the OGTT ( $AUC_{Glucagon0-120}$ ) and serum IL-33 levels among patients with or without PTDM, respectively.

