#### *Incidence and risk factors for early PTDM*

We prospectively analyzed PTDM incidence (defined as a weekly fasting glucose  $\geq 126$  mg/dL or random glucose  $\geq 200$  mg/dL) during the first 100 days of HCT in 84 patients without diabetes (1). New-onset PTDM was diagnosed in 50 (60%) patients at a median of 23 days after HCT and prior to the start of steroids in the majority. PTDM was associated with inferior survival when analyzed in a time-dependent manner [hazard ratio (HR), 3.27; 95% confidence interval (CI), 1.3-8.2;  $P=0.01$ ]. In multivariate analysis, elevated, pre-transplant fasting C-peptide level independently predicted both new-onset PTDM [odds ratio (OR), 5.9; 95% CI, 1.77-20.22;  $P=0.004$ ] and increased mortality (HR, 1.05; 95%CI, 1.01-1.09;  $P=0.013$ ) (1). This prospective study indicates that compensatory  $\beta$ -cell changes, as evidenced by increased fasting C-peptide level, could be present prior to HCT (and before exposure to immunosuppression) and that changes in glucose metabolism could lead to inferior HCT outcomes.

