## **10.0 Statistical Considerations**

### **10.1 Power Analysis and Sample Size Calculation**

#### **D.3.c. Sample size calculation for Aims 1 and 2.**

$\beta$ -cell function, glucagon suppression, and IL-33 signaling are the primary outcomes for the aims. Sample size was calculated using a 2-group t-test with PS Software (version 3.0, Dupont&Plummer, 2009) at a 0.05 two-sided significance level. We estimate a 50% incidence of PTDM by day+100 (1, 8, 14). The sample size provides at least 80% power to detect a biologically meaningful difference in mean between patients with and without PTDM for each aim. The same patient cohort will be monitored for all aims. We will enroll 34 patients to ensure at least 80% power for each aim. Assuming the dropout rate is about 10% (early death or pre-HCT diagnosis of diabetes by OGTT), an additional 6 subjects will be recruited (41-43). Forty subjects are feasible to accrue over 4 years, given that 151 patients underwent allogeneic HCT at Vanderbilt in 2015.

**Subaim 1A primary outcome: second-phase GSIS.** A mean difference of 7.5  $\mu$ U/mL represents a significant difference in second-phase insulin release between healthy controls and individuals at risk for type 2 diabetes (44-46). A sample size of 17 patients in each group (either with or without PTDM) has 80% power to detect at least a 7.5  $\mu$ U/mL difference in insulin secretion between groups using a standard deviation of 7.5  $\mu$ U/mL.

**Subaim 1B primary outcome: glucagon secretion during OGTT.** AUC was calculated for each patient to present as total glucagon secretion during OGTT. Our preliminary data observed  $8.83 \pm 0.73$  pg/mL•min (mean  $\pm$  SD) in log(AUC) scale for patients with PTDM (Figure 4). With a sample size of 9 each group, there is 80% power to detect a log(AUC) change of from 8.83 pg/mL•min to 7.83 pg/mL•min.

**Aim 2 primary outcome: IL-33 signaling** Extrapolating our preliminary and pre-clinical data, a mean difference of 70 pg/mL is likely to represent a significant difference in IL-33 signaling between groups (14, 20). With a sample size of 17 in each group, there is 80% power to detect a 70 pg/mL difference in IL-33 production between groups using a standard deviation of about 70 pg/ml.

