### *General statistical plan*

Data will be presented using means and standard deviations for continuous variables, as well as percentage and frequency for categorical variables. Investigations for outliers and assumptions for statistical analysis, e.g., normality and homoscedasticity will be made for the parametric test such as t-test and mixed model. If necessary, data will be transformed utilizing appropriate transformations such as the log or square root. Comparison between two independent groups, e.g., with or without PTDM, will be carried out using either two-sample t-test or Wilcoxon rank sum test for continuous variables and Chi-square test or Fisher's exact test for categorical variables. A Spearman correlation will be used to test the relationship between 2 continuous variables. For matched analyses and for the comparison of the changes between baseline and day+90 after transplant in the entire cohort, the mean difference will be compared with paired Student's t-test or Wilcoxon signed rank test for continuous

variables and a McNemar's test for categorical variables. To compare the differences between baseline (pre-transplant) and day +90 test results among various groups we will apply linear mixed model to continuous outcomes and generalized linear mixed model to binary/ordinal outcomes. Groups of interest will be created by stratifying patients based on PTDM, conditioning regimen (ablative vs. reduced intensity) or acute GVHD treated with steroids. All data will be stored in a computerized database and analyzed with R version 3.3.1 (R Foundation for Statistical Computing, Vienna, Austria). *P*-values will be 2-tailed and considered significant at *P* <0.05.

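### The adjusted GSIS odds ratio in Subaim 1A rests on about 17–18 PTDM events for four slopes; ordinary logistic regression would overstate a real effect, and section 10.2 should name Firth penalised likelihood

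*Combined protocol and SAP*

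**What the plan says.** Section 10.2 (Primary analysis of Subaim 1A) first compares pre-transplant GSIS between patients who do and do not develop PTDM, using a Wilcoxon rank sum test. It then adds an adjusted model: "Multivariable logistic regression will evaluate whether GSIS is an independent predictor of PTDM after adjusting for the following covariates". Three binary covariates follow (sex, ablative versus reduced-intensity conditioning, steroid-requiring acute GVHD), joined by *or*. On reporting it says: "The estimated OR and 95% CI of the OR will be provided to measure the effect of the association". The primary analyses of Aims 1B and 2 are to follow a similar approach.

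Section 10.1 supplies the size: "We will enroll 34 patients to ensure at least 80% power for each aim", with six more recruited for about 10% dropout, and "We estimate a 50% incidence of PTDM by day+100". The sizing itself rests on the unadjusted comparison: "Sample size was calculated using a 2-group t-test with PS Software", "at a 0.05 two-sided significance level".

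The General statistical plan names R 3.3.1 and says P-values "will be 2-tailed and considered significant at" the 0.05 level. Nothing in section 10 names an estimator for the logistic model, a penalty or exact method, the type of confidence interval or test, or what happens if a model fails to converge.

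**The concern.** Maximum-likelihood logistic regression is biased away from the null when events are few relative to coefficients. A sparse or empty cell in a binary covariate can also send estimates to infinity. Both conditions are foreseeable at this sample size.

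The odds ratio is the effect measure that section 10.2 names for the adjusted question, whether GSIS predicts PTDM independently. An inflated value would mislead anyone who used it to judge how strong a predictor GSIS is or to size later work. The Preliminary Data section already cites an odds ratio of this kind as rationale (5.9, 95% CI 1.77–20.22, from 84 patients). The present cohort is less than half that size.

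**Working it through.** **The plan's own figure.** The inputs, from section 10.1, are a difference of 7.5 µU/mL, SD 7.5, two-sided 0.05 and 80% power.
- Normal approximation: n per group = 2 × (1.960 + 0.842)² × (7.5/7.5)² = 15.7, so 16.
- Noncentral t: power is 78.1% at 16 per group and 80.7% at 17.

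The stated 17 per group is reproduced. It concerns the unadjusted two-group comparison only.

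**Events per slope.**
- Evaluable patients: the target is 34. Recruiting 40 with 10% loss leaves 36.
- Events at 50%: 34 × 0.5 = 17 and 36 × 0.5 = 18.
- Slopes: GSIS + 3 covariates = 4 (five parameters with the intercept).
- Events per slope: 17/4 = 4.25 and 18/4 = 4.5. If both GSIS phases entered one model, 17/5 = 3.4 and 18/5 = 3.6.
- The preliminary cohort had a higher incidence ("New-onset PTDM was diagnosed in 50 (60%) patients"). At 60% the smaller outcome class is 34 × 0.4 ≈ 14 non-PTDM patients.

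**True effect.** For a normal predictor with equal SDs, the log odds ratio per within-group SD is the standardised mean difference: 7.5/7.5 = 1.0, an odds ratio of e¹ = 2.72. The base simulation sets 1.0 per whole-cohort SD, which corresponds to a standardised group difference of about 0.91. A further run uses fixed 17/17 groups with an exact 1-SD shift.

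**Simulation.** There were 10,000 trials per setting, with standardised GSIS and three binary covariates. Values assumed because the documents do not give them: covariate prevalences 40%, 50% and 35% (GVHD 15% as a sensitivity case) and covariate log odds ratios 0 or 0.7. The last three rows of the table use 0. Means for maximum likelihood (ML) are over converged fits. Entries are log odds ratios, with exp() in brackets; exp of the mean is the geometric-mean odds ratio.

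| Setting (true 1.0, OR 2.72) | ML mean | ML median | Firth mean | Firth median |
|---|---|---|---|---|
| n=34, covariate effect 0 | 1.337 (3.81) | 1.190 (3.29) | 1.028 (2.80) | 0.949 (2.58) |
| n=34, covariate effect 0.7 | 1.365 (3.92) | 1.206 (3.34) | 1.031 (2.80) | 0.951 (2.59) |
| n=36, covariate effect 0 | 1.303 (3.68) | 1.173 (3.23) | 1.020 (2.77) | 0.948 (2.58) |
| n=36, covariate effect 0.7 | 1.326 (3.77) | 1.190 (3.29) | 1.028 (2.80) | 0.954 (2.60) |
| 17/17 fixed, 1-SD shift | 1.356 (3.88) | 1.206 (3.34) | 1.035 (2.82) | 0.960 (2.61) |
| n=34, skewed GSIS | 1.374 (3.95) | 1.198 (3.31) | 1.018 (2.77) | 0.894 (2.44) |
| n=36, 60% incidence | 1.318 (3.74) | 1.188 (3.28) | 1.028 (2.80) | 0.958 (2.61) |

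Separate runs of the base design show the spread. ML exceeds twice the true odds ratio in 23–24% of trials, Firth in 9–11%. The RMSE of the log odds ratio falls from 0.80 to 0.52 at n=36 in one run, and from about 0.88 to 0.55 in another. With one covariate at a time the ML mean is about 1.20 (OR 3.3), and 15–18% of trials exceed twice the truth.

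**No effect (true log odds ratio 0).** Both estimators are centred on zero. Rejection at nominal 5%, across all settings (Monte Carlo standard error 0.2–0.3 points):
- ML Wald: 3.4–5.0%
- ML likelihood ratio: 7.4–8.3%
- Firth penalised likelihood ratio: 4.6–5.0%

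**Separation or non-convergence under ML.** This occurs in 0.2–1.5% of trials at the base prevalences, and in about 11–18% across runs if steroid-requiring GVHD has 15% prevalence.

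**Power for the adjusted GSIS term.** In the base settings Firth gives 63–69% and ML Wald 61–68%. With the exact 1-SD shift and 17/17 groups the figures are 76% and 75%.

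**The case against.** Several objections carry weight.

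- **The plan names no likelihood-ratio test.** A reader might infer that the planned test has an inflated error rate. The documents do not support that: they promise an odds ratio and a 95% CI without giving the type, and Wald tests hold their size. The anti-conservatism is conditional on a choice not yet made.
- **The odds ratio is not the only effect size.** A reader might infer so, but section 10.2 opens with a group comparison, the General statistical plan presents means and SDs, and the sizing is on the mean difference.
- **The bias does not create an association.** A reader might infer that the odds ratio is too large whatever the truth. With no effect it is centred on 1; the bias only exaggerates a real one.
- **The covariate list is joined by *or*.** One-at-a-time adjustment is a possible reading and reduces the bias without removing it. *Multivariable* favours joint entry.
- **Firth is not the only remedy.** Steroid-requiring GVHD arises after transplant, and the Background and Preliminary Data sections say PTDM mostly precedes steroids. Dropping that covariate would save a slope. This is a fair alternative, but the one-covariate result shows that bias persists in smaller models.
- **The link to screening tools is loose.** The Rationale section says the OGTT and clamp results in general will be adapted for screening; it does not mention this odds ratio.

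None of these removes the overstatement when GSIS has a real effect, which is what Subaim 1A hypothesises.

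**Conclusion.** The point holds for the adjusted estimate. If the true odds ratio is about 2.7 per SD, unqualified logistic regression with all three covariates overstates it to a geometric mean of about 3.7–3.9 (30–37% on the log scale) and a median of about 3.2–3.3. The result is stable over skewed GSIS, 60% incidence and fixed 17/17 groups. The risk of a model that does not converge is small unless steroid-requiring GVHD is uncommon, and the plan has no rule for that case.

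The conclusion rests on reading unqualified logistic regression in R as maximum likelihood, on joint entry of the covariates, and on the assumed prevalences and covariate effects. It does not touch the Wilcoxon comparison or the 17 per group. The power figures for the adjusted model should not be set against the plan's 80%, which belongs to the unadjusted t-test. This is a cheap improvement to a reported quantity and no threat to the main comparison.

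**What to change.** In section 10.2, specify Firth penalised logistic regression for the PTDM models in Subaim 1A and the matching models in Aims 1B and 2, with profile penalised-likelihood 95% CIs and tests. Express each odds ratio per SD of the predictor. In the same place, state whether the covariates enter together or one at a time.

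The cost is one or two sentences; the method is available in R. The reported odds ratio will be noticeably smaller (geometric mean about 2.8 instead of 3.7–3.9). The median log odds ratio will sit slightly low, about 0.95 for a true 1.0 and 0.89 with skewed GSIS. Power is about the same as for the ML Wald test, so the change corrects the estimate but adds no power.

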**Subaim 1A. To determine if a compensatory increase in glucose stimulated insulin secretion (GSIS) by  $\beta$ -cells precedes PTDM development in patients without diabetes undergoing MRD HCT.** Based on our C-peptide and oral glucose tolerance test (OGTT) data, we hypothesize that PTDM-prone individuals maintain euglycemia pre-transplant via enhanced  $\beta$ -cell secretory capacity followed by progressive  $\beta$ -cell dysfunction and relative insulin insufficiency after transplant. In a prospective MRD HCT cohort without diabetes,  $\beta$ -cell function and secretory capacity will be directly measured with hyperglycemic clamps before and 90 days after transplant.

**Subaim 1B. To determine if excess glucagon secretion and impaired  $\alpha$ -cell response to glucose or GLP-1 contributes to the hyperglycemia of PTDM.** We will test the hypothesis that PTDM patients have increased glucagon levels and that glucose and GLP-1 induced  $\alpha$ -cell suppression are incomplete. To assess  $\alpha$ -cell dysregulation, glucose-induced glucagon suppression will be measured during a hyperglycemic clamp and during 2 OGTTs either with or without GLP-1 infusion, before and 90 days after HCT.

**Specific Aim 2. To determine if the IL-33/ST2 axis promotes immune/islet cell dysregulation during PTDM.** We hypothesize that PTDM is characterized by decreased protective IL-33/ST2 signaling in adipose tissue at rest (*i.e.* pre-transplant)

followed by increased systemic, inflammatory signaling during stress (*i.e.* post-transplant), which leads to  $\beta$ -cell compensation and exhaustion, respectively. To investigate the ST2 pathway, we will measure adipose and plasma levels of IL-33 and sST2 and quantify ST2 expression on circulating Tregs and Th1 cells before and after HCT from our MRD cohort. IL-33 effects on T cells and on human islet function will be assessed *in vitro*.

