#### *PTDM is Th-1 skewed and characterized by altered ST2 signaling*

[figure not shown]
Elevated fasting C-peptide levels pre-transplant and PTDM development after HCT both predict inferior survival (1, 8). Our collaborators have demonstrated that pre-transplant elevations in the decoy receptor sST2 are seen with obesity and that high sST2 after HCT is a validated biomarker for non-relapse mortality due to immune dysregulation (30-32). Published literature indicates that low IL-33 levels are involved in insulin resistance in non-transplant animal models of diabetes (21, 22). Therefore we sought to examine sST2 as a predictor of PTDM independent of GVHD. In a group of HCT recipients without preexisting diabetes, serum sST2 was elevated at neutrophil engraftment in patients who were prospectively diagnosed with new-onset PTDM after HCT (Figure 2). This increase in engraftment sST2 was confirmed in a separate cohort of HCT recipients who were retrospectively diagnosed with PTDM (14). We also confirmed that the majority of PTDM diagnoses occurred before steroids exposure (67% in cohort 1 and 93% in cohort 2). Since PTDM generally occurs before steroids then steroids should not influence the development of PTDM for the majority. After adjustment for myeloablative chemotherapy and grade 3-4 acute GVHD (factors known to influence sST2 and survival), high engraftment sST2 ( $\geq 75^{\text{th}}$  percentile of combined cohorts 1 and 2) predicted increased PTDM (HR, 2.25; 95%CI, 1.07-4.75;  $P = 0.03$ ) and non-relapse mortality risk (HR, 8.54; 95%CI, 1.62-45.15;  $P = 0.01$ ) (14). Thus, the data suggests that dysregulation of the IL-33/ST2 axis may influence metabolic complications after HCT which in turn presages clinical GVHD, steroid exposure, and mortality.

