#### *Diagnosis of PTDM*

PTDM is defined by the occurrence of a fasting blood glucose level  $\geq 126$  mg/dL or a random blood glucose level  $\geq 200$  mg/dL at any point from day +1 (day after stem cell infusion) to day +100 after transplant. Fasting blood glucose level will be assessed weekly during routine outpatient visits from day 1 to day 100 after transplant. Patients will be evaluated following an 8 hour overnight fast (water and medications allowed) during standard of care visits. Random blood glucose levels from day +1 to day +100 after transplant will be assessed during standard of care visits or during hospitalization. For hospitalized patients and patients receiving total parenteral nutrition (TPN), all blood glucose determinants will be considered random blood glucose levels for purposes of analysis.

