#### *Data Management and Safety*

All data will be collected prospectively until day 100 post-transplant. Information will be stored in a password protected electronic database. After day 100, the database will be updated when the patient is seen in the clinic for their annual visit (i.e. 1 year after transplant). In addition, the standard of care in the transplant program is to discuss complex inpatients and outpatients (within the first 100 days) on a weekly basis. Detailed minutes of these meetings are routinely maintained. Major events (e.g.: unexpected

toxicity and all deaths) are routinely reviewed in a Quality Assurance Meeting and detailed minutes are kept. The above measures will ensure that study patients are monitored closely after transplant and that data will be accurate.

A total of 550 mL of blood will be collected from the patient over approximately 110 days (over 3 to 4 months) for this study.

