### *Secondary analyses for Subaims 1A and 1B*

1) determining if glucagon secretion and OGTT results pre-transplant predict PTDM development (herein OGTT results refers to 2 hour blood glucose and peak/nadir/total hormone levels during OGTT), 2) determining if GLP-1 infusion increases insulin secretion and glucagon suppression compared to OGTT values without GLP-1, 3) comparing GSIS, glucagon suppression, and OGTT results at day +90 among patients with or without established PTDM, and 4) comparing the change in GSIS, glucagon suppression, and OGTT results at baseline to those determined at day +90 after transplant in the entire cohort or among groups stratified based on PTDM, conditioning regimen (ablative vs. reduced intensity) or for the presence or absence of acute GVHD treated with steroids.

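### The Subaim 1A logistic model adjusts pre-transplant GSIS for acute GVHD requiring steroids, a post-transplant event that may come after PTDM, so its odds ratio is not a pre-transplant prediction

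*Combined protocol and SAP*

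**What the plan says.** Section 1.0 sets Subaim 1A as finding out whether a compensatory rise in GSIS "precedes PTDM development in patients without diabetes undergoing MRD HCT". Section 10.2 (Primary analysis of Subaim 1A) compares pre-transplant GSIS between patients who do and do not later develop PTDM by a Wilcoxon rank sum test. It then says: "Multivariable logistic regression will evaluate whether GSIS is an independent predictor of PTDM", with an odds ratio and 95% CI, adjusting for "gender, conditioning (ablative vs. reduced intensity), or acute GVHD requiring steroids".

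Section 6.0 (Diagnosis of PTDM) lets PTDM occur "at any point from day +1 (day after stem cell infusion) to day +100 after transplant". Section 3.0 (Incidence and risk factors for early PTDM) reports that in an earlier cohort of 84 patients it was diagnosed "at a median of 23 days after HCT and prior to the start of steroids in the majority". A later part of section 3.0 puts the share of PTDM diagnoses made before steroid exposure at 67% in one cohort and 93% in another. It reads the metabolic changes as heralding GVHD and steroid use.

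The GVHD factor returns as a stratifier in the secondary analyses ("the presence or absence of acute GVHD treated with steroids") and in the general statistical plan. Nowhere is it given a window, a landmark, time-dependent coding or a rule that it must precede PTDM.

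**The concern.** Gender and conditioning are fixed before transplant. Acute GVHD requiring steroids is not, and nothing stops the flag from recording an event that followed the PTDM diagnosis. The model would then explain an outcome partly by something that happened later and may be a consequence of it.

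At stake is the only effect estimate that section 10.2 names for GSIS as an independent predictor. A model that needs a later event as input cannot give a risk before transplant. The GSIS coefficient may also change, if steroid-requiring GVHD is related to both PTDM and GSIS.

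The word joining the last two covariates adds an ambiguity. If all three enter together, the only adjusted model contains the flag. If they enter one at a time, models without it exist, but none is named as the main one.

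**Working it through.** **1. The plan's own figure.** Section 10.1 gives a difference of 7.5 µU/mL, SD 7.5 µU/mL, two-sided 0.05 and 17 per group for 80% power. The standardised difference is 7.5/7.5 = 1. A two-sample t-test needs n = 16.71, so 17 per group. At 17 the noncentrality is √(17/2) = 2.92 on 32 df, and power is 80.7%. The figure reproduces. It uses no covariates, so this point does not touch it.

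**2. Timing.** With 50% PTDM among 34 patients there are about 17 cases. Applying the group's shares, 0.67 × 17 = 11.4 and 0.93 × 17 = 15.8, so about 11 to 16 cases would be diagnosed before any steroid exposure. In those patients, any steroid-requiring GVHD would be recorded after the outcome.

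These are shares of all PTDM diagnoses and may include patients who never had steroids, so they do not give the order among flagged patients. If a share f of PTDM patients is flagged, steroids came first in at most 0.33/f or 0.07/f of them. At f = 0.5 (assumed) that is up to 66% or up to 14%.

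**3. Predicted risk.** The documents give no GVHD rates, so those below are assumptions. Let GSIS in SD units be N(1,1) with PTDM and N(0,1) without, with 50% PTDM. At the midpoint, GSIS alone implies a risk of 50%. If GVHD depends only on PTDM, with rates r₁ (PTDM) and r₀ (no PTDM), a model with the flag predicts r₁/(r₁+r₀) when it is set and (1−r₁)/[(1−r₁)+(1−r₀)] when it is not:

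| r₁ / r₀ | flag set | flag not set |
|---|---|---|
| 40% / 30% | 0.4/0.7 = 57% | 0.6/1.3 = 46% |
| 50% / 25% | 0.5/0.75 = 67% | 0.5/1.25 = 40% |
| 60% / 25% | 0.6/0.85 = 71% | 0.4/1.15 = 35% |

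Before transplant nobody knows which column applies.

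**4. The GSIS odds ratio.** Without the flag, the log odds ratio per SD is (1−0)/1 = 1, so the OR is e¹ = 2.72. With the flag, fitting the logistic model to the whole assumed population by numerical integration gives:

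| Link of GSIS to GVHD (log-odds per SD) | −0.7 | −0.35 | 0 | +0.35 | +0.7 |
|---|---|---|---|---|---|
| GVHD rates held at 50% / 25% | 3.56 | 3.04 | 2.72 | 2.56 | 2.52 |
| PTDM-to-GVHD OR fixed at 3 (no-PTDM rate 25%) | 3.13 | 2.95 | 2.72 | 2.49 | 2.30 |
| PTDM-to-GVHD OR fixed at 1 | 2.72 | 2.72 | 2.72 | 2.72 | 2.72 |

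There is no shift when GVHD depends on PTDM alone or on GSIS alone. When it depends on both, the OR falls or rises with the sign of the link.

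**5. Why a yes/no flag for steroids before PTDM is no remedy.** Cases stop accruing exposure at diagnosis, while non-cases accrue it to day 100. Assume no true effect, a constant start rate and a share p on steroids by day 100. With every diagnosis at day 23, the share of cases flagged is 1−(1−p)^0.23:

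| p | cases flagged by day 23 | spurious OR |
|---|---|---|
| 25% | 6.4% | 0.21 |
| 40% | 11.1% | 0.19 |
| 50% | 14.7% | 0.17 |

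Placing all diagnoses at day 23 exaggerates the effect. Spreading them over days 1 to 100 with the same median gives 0.21 to 0.26 (truncated exponential) or 0.26 to 0.32 (piecewise uniform). A fair summary is about 0.2 to 0.3, still well below 1.

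**The case against.** The strongest reply is that the model is associational. Section 10.2 offers the OR as a measure of association and takes a similar approach to glucagon and IL-33 measured after transplant. On that view, calling GSIS an independent predictor is conventional wording, and any informative covariate splits predicted risk. The covariate also has a rationale: section 2.0 argues that PTDM is more than a drug effect, and the group's earlier sST2 analysis adjusted for grade 3-4 acute GVHD. Part of this stands. Asking whether GSIS matters apart from steroid-requiring GVHD is legitimate, and the choice is partly one of estimand. But a flag that may count steroids started after PTDM does not answer that question either, and Subaim 1A is explicitly about what comes before PTDM.

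Several stronger readings are tempting, and the documents do not support them:

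- **The flag will pick up GVHD after day 100.** A reader might infer this from "After day 100, the database will be updated when the patient is seen in the clinic for their annual visit" and from the day 365 and day 730 columns of Appendix A. The same part of section 6.0 says that data collection is prospective up to day 100, which makes that the natural window. What remains is the unspecified order within days 1 to 100.
- **Most flagged patients had PTDM first.** The 67% and 93% figures do not establish this (step 2).
- **The GSIS odds ratio is biased.** It may be, but neither the fact nor the direction follows from the documents.
- **The primary comparison or the power fails.** The Wilcoxon test and the 17-per-group calculation do not use the covariate.
- **Subaim 1B and Aim 2 share the fault.** Their primary measures are taken after transplant, so the mismatch with a pre-transplant question does not arise.

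**Conclusion.** The point holds for any Subaim 1A model that contains the GVHD covariate. This is more than missing detail: a model meant to show that pre-transplant GSIS predicts PTDM conditions on a later event that, on the group's own data, may follow the outcome. Its odds ratio cannot be read as a pre-transplant prediction, even if the number does not move.

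The numerical effect is unknown. Under the assumed rates and links the OR stays at 2.72 per SD or lies between about 2.3 and 3.6, with the direction open. Confidence is high on the timing and interpretation, and no claim is made about actual bias. The model should be corrected before analysis, but the unadjusted primary comparison stands as planned.

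**What to change.** In section 10.2 (Primary analysis of Subaim 1A), state that the main logistic model adjusts only for covariates fixed before transplant: gender and conditioning (ablative or reduced intensity), entered together. This also settles how the covariates enter.

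Add a sentence saying that a labelled sensitivity analysis will include acute GVHD requiring steroids, counted to day 100, and that its odds ratio is explanatory and not a pre-transplant prediction. Steroid start is best treated there as time-dependent, for example in a time-to-PTDM model, though with about 17 events this can stay optional. Avoid a yes/no flag for steroids before PTDM, for the reason in step 5.

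The cost is one line and one sentence. No new data are needed unless the time-dependent version is used. That version needs PTDM and steroid start dates, which the chart review planned in section 6.0 should be able to supply. With GSIS entered as one term, 17 events per term rises from 17/4 = 4.25 to 17/3 = 5.67. The downside is that steroid-related PTDM is addressed only in the sensitivity analysis.
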